**Document History**

Version	Date	Change(s)	Author
0.1		Initial Draft	
0.2			
1.0	04MAR2020	Final Version	[name]

## 1. PROTOCOL SYNOPSIS

Title	Safety of Donor Alloantigen Reactive Tregs (darTregs) to Facilitate Minimization and/or Discontinuation of Immunosuppression in Adult Liver Transplant Recipients ( ARTEMIS )
Short Title	darTregs for CNI Reduction
Protocol Number	CTOTC-12
ClinicalTrials.gov Identifier	NCT02474199
Clinical Phase	Phase I/II
Primary Safety Objective	This study will evaluate the safety and tolerability of a single IV dose of the darTregs product.
Secondary Safety Objective	This study will evaluate the safety of immunosuppression (IS) 1) minimization and 2) discontinuation after one IV dose of darTregs.
Primary Efficacy Objective	The study will evaluate the ability of a single IV dose of darTregs to reduce baseline, standard of care (SOC) calcineurin inhibitor (CNI) dosing by 75% along with discontinuation of either prednisone or mycophenolate mofetil (MMF), as applicable.
Secondary Efficacy Objective	This study will determine whether a single IV dose of darTregs can induce operational tolerance.
Mechanistic Objectives	We will assess the pharmacokinetic profile of darTregs by measuring the level of deuterium-labeled Tregs in circulation. Potential impact of darTregs therapy on immunological profiles will be assessed by comparing leukocyte phenotypes, tissue histology and gene expression in protocol and for-cause biopsies, and alloantibody before and after darTregs infusion.
Study Design	A multi-center, open-label clinical trial in adult liver transplant recipients with two primary interventions: 
 
• administration of a single IV dose of darTregs and
 
• reduction of IS dosing with possible complete IS discontinuation.
 
 Adult living donor liver recipients two to six years after LT will initiate IS withdrawal. Twelve to 14 weeks later, they will receive a single dose of darTregs and continue IS withdrawal.
Primary Safety Endpoint	The safety and tolerability of a single infusion of darTregs administered to LT recipients will be assessed 24 weeks after darTregs by describing: 
 
1. Occurrence of CTCAE Grade 3 or higher adverse events (AEs) attributable to the darTregs infusion including infusion reaction / cytokine release syndrome
 
2. Occurrence of study defined Grade 3 or higher infections
 
3. Occurrence of any malignancy, including PTLD
 

Secondary Safety Endpoint	The trial will assess the safety of IS withdrawal in the context of darTregs therapy by describing the following secondary safety endpoints: 
 
1. Rate of composite outcome measure including refractory acute rejection, chronic rejection, re- transplantation, and death
 
2. Incidence of biopsy proven or clinical acute rejection and/or chronic rejection
 
3. Timing of biopsy proven or clinical acute rejection and/or chronic rejection
 
4. Severity of biopsy proven acute rejection and/or chronic rejection
 

Primary Efficacy Endpoint	The efficacy of a single IV dose of darTregs will be assessed by the number and proportion of LT subjects who are able to reduce CNI dosing by 75% and discontinue a 2 nd IS drug (if applicable) with stable liver tests for at least 12 weeks. The frequency of successful CNI minimization will be compared to historical cohorts of comparable adult LT recipients undergoing IS withdrawal.
Secondary Efficacy Endpoints	The efficacy of a single IV dose of darTregs infusion will be assessed by determining the number and percentage of subjects who have received darTregs and are identified as operationally tolerant, defined by maintaining stable allograft function (assessed by liver tests) and histology (determined by central pathologist reading in comparison to screening liver biopsy at study entry) in the absence of IS for one year. The frequency of tolerance will be compared to historical cohorts of adult liver transplant recipients undergoing IS withdrawal.
Primary Mechanistic Endpoints	The level and persistence of deuterium-labeled darTregs in the circulation will be determined by serial measurements of deuterium content in DNA from purified peripheral blood Tregs after darTregs infusion using gas chromatography-mass spectrometry (GC-MS) testing.
Secondary Mechanistic Endpoints	The overall increase of darTregs in circulation will be assessed using the alloreactive T cell frequency (ATF) assay
Exploratory Mechanistic Endpoints	The immunologic impact of infused darTregs will be determined by assessing the following: 
 
Leukocyte phenotypes before and after darTregs infusion using multi-parameter flow cytometry (MFC).
 
Alloantibody responses before and after darTregs infusion during IS withdrawal.
 
Histology and multiplex immunohistochemistry of protocol and for cause biopsies
 
The composition of immune infiltrate in liver biopsies post Treg infusion and at the time of for-cause biopsies will be profiled using single-cell RNA+TCRseq
 

Accrual Objective	Up to 18 participants will be screened and enrolled to target up to 11 participants eligible for both IS withdrawal and darTregs infusion
Study Duration	The maximal length of trial participation for an individual subject is anticipated to be 2 years. The total trial duration will be 3 years. 
 
One year period to accrue nine patients eligible for both IS withdrawal and darTregs infusion that will be given approximately 10-11 weeks after initiating IS withdrawal
 
Minimum of 52 weeks follow-up after any AR episode or darTregs infusion
 
For all subjects able to discontinue IS, 52 weeks of follow-up after the last IS dose to assess for operational tolerance
 
 The duration of study participation will vary by subject depending on his/her duration of IS withdrawal. Accounting for a one year enrollment period, the primary endpoint for all participants will be assessed approximately 1.5 years after trial initiation.
Treatment Description	All eligible participants will initiate IS withdrawal. Approximately 10-12 weeks after initiating IS withdrawal, subjects will have autologous Tregs collected for darTregs manufacturing. 
During the last 2 weeks of IS withdrawal Step 2 (CNI reduced by 25%), a single total dose of 400 x 10^6 ± 100 deuterium-labeled darTregs will be infused intravenously. The subject will then, if eligible, resume IS withdrawal within 2 weeks after darTregs infusion (see Section entitled "Resumption of IS Withdrawal after darTregs Infusion" below). Only subjects who receive 300-500 x 10^6 darTregs and who meet the primary endpoint of 75% reduction in CNI from baseline after darTregs will be offered the opportunity to continue IS withdrawal until complete discontinuation of IS (secondary endpoint). Those who receive 100-300 x 10^6 darTregs will only be allowed to proceed to the primary endpoint but will not be eligible for complete IS withdrawal.

Study Enrollment/ IS Withdrawal Inclusion Criteria	
Subjects who meet all of the following criteria are eligible for enrollment as study participants:
 

1. Able to understand and provide informed consent

2. Have received primary, solitary, living donor liver transplant more than 24 months but less than 84 months ago

3. Have a living donor who is willing to consent to one time phlebotomy of 100 mLs to enable manufacture of darTregs

4. Between 18 and 70 years of age at the time of study entry/consent

5. Have ALT consistently <60 U/L and either alkaline phosphatase consistently <150 U/L or GGT consistently <60 U/L

6. Currently receiving a calcineurin inhibitor (CNI) with 12 hour trough levels consistently <6.0ng/mL for tacrolimus; <150ng/mL for cyclosporine

7. Currently receiving CNI monotherapy or CNI and ONE of the following:

a. Prednisone: maximum dose of 5mg / day

b. Mycophenolate mofetil (MMF): maximum dose of 500mg bid for Cellcept or 360mg bid for Myfortic

8. Female and male subjects with reproductive potential must agree to use effective methods of birth control for the duration of the study

9. If history of HCC, LT recipients who have:

a. AFP less than 100 µg/L at the time of transplant AND

b. Implanted liver:

i. with tumor burden within the Milan criteria and

ii. without macro- or micro-vascular invasion and

iii. without any lesions with poorly differentiated HCC and

iv. without cholangiocarcinoma morphology

c. Risk Estimation of Tumor Recurrence After Transplant (RETREAT) Score less than or equal to 3

10. If history of HCC, at the time of enrollment, subjects must also:

a. Be 36 months or more post-transplant AND

b. Without evidence of recurrent HCC defined as

i. AFP within normal limits for performing laboratory

ii. Confirmatory chest CT and

iii. Confirmatory CT or MRI of the abdomen and pelvis

11. If history of HCV, recipients must be:

a. Cured of HCV as defined by achieving SVR and be greater than or equal to six months after the end of treatment

b. HCV RNA negative at time of study enrollment

--	---

Study Enrollment/ IS Withdrawal Exclusion Criteria	
Subjects who meet any of these criteria are not eligible for study enrollment.
 
 
1. Transplant for liver disease secondary an autoimmune etiology (e.g. autoimmune hepatitis, primary sclerosing cholangitis, or primary biliary cirrhosis)
 
2. Matched at both HLA-DR loci to the donor
 
3. Organ, tissue or cell transplant prior to or after the primary solitary living donor liver transplant
 
4. For subjects with hepatitis B, detectable HBV DNA
 
5. History of malignancy within 5 years of enrollment. History of adequately treated in-situ cervical carcinoma and/or skin cancer (basal or squamous cell) will be permitted.
 
6. Serologic evidence of human immunodeficiency 1 or 2 infection
 
7. Epstein Barr Virus (EBV) sero-negativity (EBV naïve) if living donor is EBV sero-positive
 
8. Cytomegalovirus (CMV) sero-negativity (CMV naïve) if living donor is CMV sero-positive
 
9. Calculated GFR less than 50 mL/min/1.73m^2 at the time of enrollment
 
10. An episode of AR within one year of enrollment
 
11. Systemic illness requiring or likely to require recurrent or chronic IS drug use
 
12. Any chronic condition for which anti-coagulation cannot be safely interrupted for liver biopsy
 
13. Positive pregnancy test
 
14. Participation in any other studies that involved investigational drugs or regimens in the preceding year
 
15. Any other condition, in the investigator's judgment, that increases the risk of darTregs infusion or prevents safe trial participation
 
16. Unwilling or unable to adhere to study requirements and procedures
 
17. Screening liver biopsy with any of the following histological criteria, as determined by the reading of a central pathologist (Table 9)
 

darTregs Infusion Inclusion Criteria	
Subjects will initiate IS withdrawal and, at the beginning of the 2nd step of the withdrawal algorithm (week 1-2), undergo a final assessment to ensure eligibility for darTregs infusion. Subjects must meet the following criteria to receive darTregs infusion:
 
 
1. Stable liver tests, defined as ALT and either alkaline phosphatase or GGT either within normal limits OR <1.5 X baseline
 
2. No detectable circulating EBV or CMV DNA prior to darTregs infusion, assessed at the time of PBMC collection for manufacture
 
3. For subjects with HBV, no detectable circulating HBV DNA prior to darTreg infusion, assessed at the time of PBMC collection for manufacture
 
4. Able to understand and provide informed consent
 

darTregs Infusion Exclusion Criteria	
Subjects who meet any of these criteria are not eligible for darTregs infusion:
 
 
1. Diagnosis of AR after initiation of IS withdrawal
 
2. Any vaccination given within 28 days prior to Treg collection for Treg production
 
3. Receipt of a vaccination within 14 days prior to Treg infusion
 
4. Unacceptable darTregs product
 
5. Positive pregnancy test
 
6. Clinical evidence of viral syndrome less than 7 days prior to darTregs infusion
 

Field Code Changed

Eligibility Criteria to Resume IS Withdrawal after darTregs infusion	Subjects are eligible to resume IS withdrawal after darTregs infusion if all criteria below are met: 1. Subject received at least $100 \times 10^6$ darTregs 2. ALT and either alkaline phosphatase or GGT remain within normal limits or $\leq 1.5 \times$ baseline after darTregs infusion 3. For subjects with elevated liver tests as defined above, local pathology reading of liver biopsy 6-10 days after darTregs infusion is without acute rejection according to Banff criteria 4. IS withdrawal resumes no later than 14 days after darTregs infusion 5. Site principal investigator determines it is acceptable for the study subject to resume IS withdrawal
Study Stopping Rules	If one of the following events occurs any time during the study, the study will be paused for DSMB review: 

• Death or graft loss

• Chronic Rejection

• Severe AR (histological or steroid refractory rejection)

 If any of the following events occurs after darTregs infusion, the study will be paused for DSMB review: 

• CTCAE Grade 3 or higher AEs attributable to the darTregs infusion including infusion reaction/cytokine release syndrome in 2 subjects

• Any infections of Grade 3 or higher as defined in Section 14.3.1

• Any malignancy, including PTLD

 Failure to manufacture and supply the cellular product for 2 subjects will also require a pause in the trial.

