## 6. STUDY OPERATIONS

### 6.1. Protocol Deviations

Protocol deviations will be listed by site with information such as type of deviation, severity of the deviation (major or non-major), date of occurrence, and the reason for the deviation. Protocol deviations will be summarized in tabular format by type of deviation.

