**Table 7-1 Visit Windows**

High Frequency SOE Visit Windows	
Study Visit	Visit Window
Study Entry Eligibility Screening Visit (Screen 1)	Eligibility labs and biopsy should be within 8 weeks prior to initiation of IS withdrawal
Remote Visits (Telephone and Local Liver Tests)	± 3 days
Transplant Center Visits	± 14 days
Recipient PBMC Collection for Manufacturing	17 (UCSF) or 18 (Mayo) days before darTreg infusion
Medium Frequency SOE Visit Windows	
Study Visit	Visit Window
Entry into Medium Frequency SOE	Within 2 weeks after rejection (Appendix 7) Within 4 weeks after completing high frequency SOE (Appendix 8)
Week 2 (Appendix 7)	± 3 days
Remote Visits (Telephone and Local Liver Tests)	± 5 days
End of Study	± 14 days
darTregs Infusion SOE Visit Windows	
Study Visit	Visit Window
darTregs Eligibility Screening Visit	Between day 14-41 of the 2 nd withdrawal step (10-13 weeks)
Treg Blood Draw for darTregs manufacturing	Between day 18-45 of the 2 nd withdrawal step
Day 0 = darTregs Infusion	During the last 2 weeks of the 2 nd withdrawal step
Day 1 after darTregs infusion	± 1 hour
Protocol biopsy visit after darTregs infusion	Between 6-10 days after darTregs infusion
Resumption of IS withdrawal	Between day 1-14 after darTregs infusion; corresponds to between day 36 – day 63 of the 2 nd withdrawal step
Day 14 after darTregs infusion	± 2 days

Unscheduled visits may also occur throughout the study. All data will be included in analyses, regardless of time of assessment.

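### Do the conflicting darTregs infusion times in the synopsis and Table 7-1 call for a change to the analysis plan?

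*SAP*

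**What the plan says.** **Synopsis (Section 1).**
- Study Duration: "darTregs infusion that will be given approximately 10-11 weeks after initiating IS withdrawal".
- Study Design: "Twelve to 14 weeks later, they will receive a single dose of darTregs and continue IS withdrawal".
- Treatment Description: "Approximately 10-12 weeks after initiating IS withdrawal, subjects will have autologous Tregs collected for darTregs manufacturing".
- darTregs Infusion Inclusion Criteria: at the start of the second "step of the withdrawal algorithm (week 1-2), undergo a final assessment to ensure eligibility for darTregs infusion".
- Criteria to resume withdrawal: "IS withdrawal resumes no later than 14 days after darTregs infusion" and, for subjects with elevated liver tests, "local pathology reading of liver biopsy 6-10 days after darTregs infusion is without acute rejection".

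**Table 7-1 (Section 7.1.2).**
- Recipient cell collection is "17 (UCSF) or 18 (Mayo) days before darTreg infusion".
- In days of withdrawal Step 2, the eligibility visit is on day 14-41 (also labelled 10-13 weeks) and the blood draw on day 18-45.
- Infusion is in the last two weeks of the step.
- Resumption is 1-14 days after infusion, which the table equates with day 36-63.
- The text below the table keeps all data in the analyses whatever the time of assessment.

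**Section 6.1.** "Protocol deviations will be listed by site with information such as type of deviation, severity of the deviation", together with date and reason. The section does not say which windows define a timing deviation.

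**The concern.** A reader who wants to know when infusion is due finds two synopsis ranges with no week in common. One of them lies within the range given for collecting the cells from which the product is made. Table 7-1 ought to settle the matter, but its draw, infusion and resumption rows do not fit together on a plain reading. The eligibility assessment also has two different windows.

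Two consequences would matter if they were real. The same infusion could be called on time or late depending on which entry is used, which would make the deviation listing arbitrary. And if day 63 were enforced as a limit, a subject infused late who was waiting for a biopsy might be stopped from resuming withdrawal. That subject could not complete Step 5 and would count as a failure on the primary efficacy endpoint (Section 7.2.1).

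**Working it through.** **1. Synopsis times in weeks.** Infusion = collection + lead time.
- Earliest: 10 + 17/7 = 12.4 weeks.
- Latest: 12 + 18/7 = 14.6 weeks.

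This overlaps the 12-14 weeks in Study Design and does not reach the 10-11 weeks in Study Duration. So the entries disagree; the arithmetic does not show which one carries the intended schedule.

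**2. Table 7-1, forward from the draw row (day 18-45).**

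| Lead | Infusion day | Resumption at +1 day, both ends | Resumption at +1 to +14 days |
|---|---|---|---|
| 17 days | 35-62 | 36-63 | 36-76 |
| 18 days | 36-63 | 37-64 | 37-77 |

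The table's own 36-63 is reproduced exactly by the 17-day lead with one day added at both ends: 18 + 17 + 1 = 36 and 45 + 17 + 1 = 63. The windows 14-41, 18-45 and 36-63 all have the same width (27 days by difference), which suggests that they were built by shifting one window along. A full allowance of 1-14 days does not give 36-63.

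**3. Table 7-1, backward from the resumption row.**
- If day 63 is the 14th day after infusion, the last infusion is day 63 - 14 = 49. Draws on days 33-45 (17-day lead) or 32-45 (18-day lead) would then lead to a later infusion.
- If day 63 is the first day after infusion, the last infusion is day 63 - 1 = 62, which agrees with the draw row at the 17-day site.

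A last infusion day of 49 is therefore one reading and not what the table must mean.

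**4. What fails even on the more favourable reading.**
- At the 18-day site a day-45 draw gives infusion on day 63 and earliest resumption on day 64. This affects 1 of the 28 draw days.
- A biopsy at least 6 days after infusion falls by day 63 only if infusion is by day 63 - 6 = 57. Infusion on days 58-62 (5 of 28) or 58-63 (6 of 28) puts it later.

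**5. The infusion row.** Its two weeks conflict with a four-week spread of infusion days only if Step 2 has a fixed length, which the SAP does not state. If the step ends when withdrawal resumes, an infusion followed by resumption within 14 days always falls in that subject's last two weeks.

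**6. Table days in weeks.** This needs an assumption. The 10-13 week label puts the start of Step 2 at week 7.0 to 8.0, depending on how it is read. Infusion on day 35 is then week 12.0-13.0, and on day 63 week 16.0-17.0. The table thus starts after Study Duration's range and can run past the 14 weeks in Study Design.

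**7. Eligibility assessment.** Weeks 1-2 (days 1-14) and days 14-41 share day 14 only.

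**8. Where these times enter an analysis.**
- Analysis samples (Section 4): defined by biopsy, start of withdrawal, receipt of darTregs and cell count.
- Primary efficacy (Section 7.2.1): Step 5 completed and at least 12 weeks of stable liver tests.
- Primary safety (Section 7.3): assessed 24 weeks after the infusion itself.
- Time off immunosuppression (Section 7.4.2): counted from completion of withdrawal.

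None uses the planned week of infusion or a Table 7-1 window.

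**The case for a change.** The case for acting is that the conflicts stand in current SAP text and no allowance for approximate wording removes them. On this view an analyst who programs timing deviations needs one set of windows, all the more because the lead time differs by site and deviations are listed by site. In a trial this small, one subject moved from success to failure is 1/18 = 5.6 or 1/11 = 9.1 percentage points of the primary proportion, if the analysed number lies between the two accrual figures in the synopsis.

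The first part stands: the entries disagree and must be brought into line. The rest does not carry through.
- Section 6.1 lists deviations from the protocol, each with its type, severity and reason. It does not say that they are computed from Table 7-1 or the synopsis.
- The criteria to resume withdrawal contain no Step 2 day limit, and nothing in the SAP makes day 63 a bar to resuming.
- Those criteria must all be met, and one of them already requires liver tests within stated limits. So even without day 63 it is not secure that a subject whose tests are elevated could resume.
- The 5.6 and 9.1 points are simply one over the sample size for a hypothetical subject. The SAP gives no way to count any such subject.

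**Conclusion.** The contradiction is real, but it is clerical. The synopsis holds infusion times of about 10-11 and 12-14 weeks, against 12.4-14.6 weeks implied by collection plus lead time. Table 7-1 overruns its own limit by one day at the 18-day site after the latest draw, and its 14-day allowance cannot be used in full after late draws. The eligibility assessment windows share one day. These passages must be reconciled with each other; this review does not say which timing is right.

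No change to the analysis plan follows. The conflicts sit in a restated synopsis and in a window table that selects no data and defines no endpoint. Correcting them would alter no analysis set, method or estimate. Two assumptions bear on this: that deviations are judged against the protocol, as Section 6.1 indicates, and that day 63 is a visit window and not a rule for stopping withdrawal, since the SAP nowhere makes it one.

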## 2. INTRODUCTION

This statistical analysis plan includes pre-planned analyses related to the study objectives outlined in the protocol.

### 3. GENERAL ANALYSIS AND REPORTING CONVENTIONS

The following analyses and reporting conventions will be used:

- Categorical variables will be summarized using counts (n) and percentages (%) and will be presented in the form "n (%)." Percentages will be rounded to one decimal place.
- Numeric variables will be summarized using n, mean, standard deviation (SD), median, minimum (min), maximum (max). The min/max will be reported at the same level of significance as original data. The mean and median will be reported at one more significant digit than the precision of the data, and SD will be reported at two more significant digits than the precision of the data.
- The median will be reported as the average of the two middle numbers if the dataset contains an even number of observations.
- Test statistics including  $t$  and  $z$  test statistics will be reported to two decimal places.
- $P$ -values will be reported to three decimal places if greater than or equal to 0.001. If less than 0.001, the value will be reported as "<0.001." A  $p$ -value can be reported as "1.000" only if it is exactly 1.000 without rounding. A  $p$ -value can be reported as "0.000" only if it is exactly 0.000 without rounding.

If departures from these general conventions are present in the specific evaluations section of this SAP, then those conventions will take precedence over these general conventions.

